4.4.2 Disallowed therapies

Per Section 7.7.1 of the Protocol, prohibited and/or restricted medications taken prior to study treatment administration and during the study are described below. Medications taken within 4 weeks prior to study treatment administration and during study treatment must be recorded on the case report form (CRF).

1. Prior exposure to BIIB092.
2. Within 4 weeks of screening or anticipated during the 52-week double-blind portion of the study, concurrent treatment with memantine; acetylcholinesterase inhibitors; antipsychotic agents or mood stabilizers (e.g., valproate, lithium); or benzodiazepines are disallowed, with the following exceptions:
 - a. Low dose lorazepam or other short-acting medications may be used for sedation prior to MRI scans for those participants requiring sedation. At the discretion of the Investigator, 0.5 to 1 mg may be given orally prior to scan with a single repeat dose given if the first dose is ineffective. Neuropsychological testing may not be performed on the same day of lorazepam administration. Participants and caregiver must be informed of risks of lorazepam use prior to administration.
 - b. Participants who take short-acting benzodiazepines or other hypnotics (e.g., temazepam, zolpidem) for sleep may continue to do so if they have been on a stable dose for 30 days prior to screening.
 - c. Clonazepam may be used for treatment of restless legs syndrome, dystonia, or painful rigidity associated with PSP if the dose has been stable for 60 days prior to screening.
 - d. Quetiapine or clozapine may be permitted if at a stable dose for at least 60 days prior to screening.
3. Receipt of systemic corticosteroids within 30 days prior to screening.
4. Receipt of an investigational immunomodulator or mAb within 180 days (or 5 half-lives, whichever is longer) prior to screening.
5. Treatment with any other investigational drugs (e.g., salsalate) including placebo or devices within 90 days prior to screening.

The incidence of disallowed medications will be summarized. A listing of subjects who took any disallowed medications will be provided.

4.5 Protocol Deviations

Protocol deviations identified during site monitoring will be captured in a Protocol Deviation log and categorized as key or non-key deviations based on Protocol Deviation Classification Form. The key protocol deviations will be summarized by treatment group. Listings will be generated for the key or non-key protocol deviations, respectively.

5 EFFICACY DATA

5.1 General Considerations

All efficacy analyses will be performed on the ITT population. In addition, the primary and the key secondary endpoints will also be performed on the PP population.

The primary, sensitivity and supplementary analyses for the primary and key secondary endpoints are listed in the below table.

Table 1 Analysis for Primary and Key Secondary Endpoints

| Endpoint | Analysis | Analysis Population | SAP Section |
|---|--|----------------------------|--------------------|
| 28-item PSPRS total score, 15-item PSPRS total score | Primary: Analysis of change from baseline at Week 52 (MMRM) | ITT | 5.2.3 |
| | Sensitivity: Copy increment from reference method (MMRM) | ITT | 5.2.4.1 |
| | Sensitivity: Jump to reference method (MMRM) | ITT | 5.2.4.2 |
| | Sensitivity: Imputation by natural disease progression (ANCOVA) | ITT | 5.2.4.3 |
| | Sensitivity: Tipping point analysis (ANCOVA) | ITT | 5.2.4.4 |
| | Sensitivity: Pattern mixture model (MMRM) | ITT | 5.2.4.5 |
| | Supplementary: PSPRS subscale analysis (MMRM) | ITT | 5.2.5.1 |
| | Supplementary: Time to clinical outcome analysis (Kaplan Meier analysis and Cox proportional hazard model) | ITT | 5.2.5.2 |
| | Supplementary: Censoring after intercurrent events (MMRM)* | ITT | 5.2.5.3 |
| | Supplementary: Per-protocol analysis (MMRM) | Per-protocol | 5.2.5.4 |
| | Supplementary: Responder analysis (Logistic regression) | ITT | 5.2.5.5 |

| | | | |
|---|---|--------------|---------|
| | Supplementary: Slope analysis (MMRM) | ITT | 5.2.5.6 |
| | Supplementary: Divergence effect analysis (MMRM) | ITT | 5.2.5.7 |
| MDS-UPDRS Part II, PSP cognitive composite battery, PSP-QoL | Primary: Analysis of change from baseline at Week 52 (MMRM) | ITT | 5.3.1.1 |
| | | | 5.3.1.3 |
| | | | 5.3.1.4 |
| | Sensitivity: Pattern mixture model (MMRM) | ITT | 5.3.1.5 |
| | Supplementary: Censoring after intercurrent events (MMRM)* | ITT | 5.3.1.5 |
| | Supplementary: Per-protocol analysis (MMRM) | Per-protocol | 5.3.1.5 |
| | Supplementary: Slope analysis (MMRM) | ITT | 5.3.1.5 |
| Supplementary: Divergence effect analysis (MMRM) | ITT | 5.3.1.5 | |
| Supplementary: Subscale analysis for PSP cognitive composite battery (MMRM) | ITT | 5.3.1.5 | |
| CGI-C | Primary: Analysis at Week 52 (MMRM) | ITT | 5.3.1.2 |
| | Sensitivity: Pattern mixture model (MMRM) | ITT | 5.3.1.5 |
| | Supplementary: Censoring after intercurrent events (MMRM)* | ITT | 5.3.1.5 |
| | Supplementary: Per-protocol analysis (MMRM) | Per-protocol | 5.3.1.5 |
| | Supplementary: Slope analysis (MMRM) | ITT | 5.3.1.5 |
| | Supplementary: Divergence effect analysis (MMRM) | ITT | 5.3.1.5 |

* Analysis excludes data collected after the intercurrent event of premature discontinuation of the study treatment. All other analyses will include data collected after intercurrent events [ICH E9 (R1) Addendum 2017].

5.1.1 Visit windows for mapping efficacy endpoint

For efficacy data that are summarized or analyzed by visit, data collected on all scheduled visits and all unscheduled visits will be mapped to an appropriate analysis visit using the windowing scheme shown in Tables 2-6. If there are 2 or more assessments available in the same analysis window for a subject, the assessment that is closest to the target visit day will be used for analysis. If there are 2 or more assessments in the same analysis window with the same distance from the target visit day, the later assessment will be used.

Table 2 Visit Windows for Primary Endpoint: PSPRS

| Analysis visit | Target visit day | Analysis visit window |
|-----------------------|-------------------------|--|
| Baseline | 1 | Most recent non-missing value on or prior to the first dose date |
| Week 12 | 85 | [43, 126] |
| Week 24 | 169 | [127, 210] |
| Week 36 | 253 | [211, 294] |
| Week 48 | 337 | [295, 350] |
| Week 52 | 365 | [351, 378] |

Table 3 Visit Windows for Key Secondary Efficacy Endpoints (MDS-UPDRS, CGI, PSP cognitive composite battery, and PSP-QoL) and RBANS

| Analysis visit | Target visit day | Analysis visit window |
|-----------------------|-------------------------|--|
| Baseline | 1 | Most recent non-missing value on or prior to the first dose date |
| Week 12 | 85 | [43, 126] |
| Week 24 | 169 | [127, 210] |
| Week 36 | 253 | [211, 308] |
| Week 52 | 365 | [309, 378] |

Table 4 Visit Windows for Other Secondary Efficacy Endpoints: SEADL, Phonemic Fluency Test, WAIS-IV Letter Number Sequencing Task, Color Trails test, and MoCA

| Analysis visit | Target visit day | Analysis visit window |
|-----------------------|-------------------------|--|
| Baseline | 1 | Most recent non-missing value on or prior to the first dose date |
| Week 12 | 85 | [43, 126] |
| Week 24 | 169 | [127, 210] |
| Week 36 | 253 | [211, 294] |
| Week 48 | 337 | [295, 434] |

Table 5 Visit Windows for Tertiary/Exploratory endpoints: [REDACTED] and [REDACTED]

| Analysis visit | Target visit day | Analysis visit window |
|----------------|------------------|---|
| Baseline | 1 | Most recent non-missing value on or prior to the first dose date, except for [REDACTED] |
| Week 24 | 169 | [85, 252] |
| Week 48 | 337 | [253, 434] |

Table 6 Visit Windows for volumetric MRI

| Analysis visit | Target visit day | Analysis visit window |
|----------------|------------------|-----------------------|
| Baseline | 1 | <=84 |
| Week 24 | 169 | [85, 252] |
| Week 52 | 365 | [281, 448] |

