6.3.1 Quantitative analyses

Actual values, change from baseline and percent change from baseline will be summarized by visit for hematology, blood chemistry, coagulation (INR and prothrombin time), and the urinalysis parameters specific gravity and pH (actual values over time only). Number of evaluable subjects, mean, standard deviation, median, 25% and 75% quartiles, minimum and maximum values will be presented at each visit. Plots of mean values (with standard error) for actual values at each visit will be provided; mean values at timepoints where n < 20 will not be plotted.

Visit windows for by visit summaries

For laboratory by visit summaries, the analysis visit should be defined using visit windows (see Table 8).

Table 8 Visit Windows for Laboratory by Visit Summaries

| Analysis visit | Target visit day | Analysis visit window |
|---|------------------|--|
| Baseline | 1 | Most recent non-missing pre-dose value |
| Week 4 | 29 | [1 (post-dose only), 42] |
| Week 8 | 57 | [43, 70] |
| Week 12 | 85 | [71, 126] |
| Week 24 | 169 | [127, 210] |
| Week 36 | 253 | [211, 294] |
| Week 48 | 337 | [295, 350] |
| Week 52 | 365 | [351, the end day of the placebo-controlled period*] |
| * The end day of the placebo-controlled period is the last day before the first dose in OLE for subjects who enter OLE, and is the last day in study for subjects who do not enter OLE. | | |

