6.4 ECGs

All individual values for QT interval, QT interval corrected for heart rate by Bazett's formula (QTcB), and QT interval corrected for heart rate by Fridericia's formula (QTcF) will be presented in the data listings. QT, QTcB, and QTcF will also be included in the summary statistics.

All available non-missing values of ECG parameters should be used in the listings, summaries, and analyses for the double-blind and open-label treatment periods. However, if QTcF is missing and RR interval in seconds is available, then QTcF will be calculated as

$$QTcF = \frac{QT}{RR^{1/3}}$$

If both QTcF and RR in seconds are missing, then QTcF will be calculated as

$$QTcF = \frac{QT}{(60/HEART\ RATE)^{1/3}}$$

Although all recorded ECG parameter values, including abnormal ECG findings, will be included in the data listings, only quantitative values recorded at or near scheduled time points will be included in the summary statistics (see Table 10).

Table 10 Visit Windows for ECG

| Analysis visit | Target visit day | Analysis visit window |
|---|------------------|---|
| Baseline | 1 | Most recent non-missing pre-dose value |
| Week 24 | 169 | [1 (post-dose only), 266] |
| Week 52 | 365 | [267, the end day of the placebo-controlled period *] |
| * The end day of the placebo-controlled period is the last day before the first dose in OLE for subjects who enter OLE, and is the last day in study for subjects who do not enter OLE. | | |

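### The Week 52 efficacy window in placebo-controlled SAP Tables 2 and 3 stops at Day 378, so pre-extension assessments on Days 379-406 map to no visit

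*SAP*

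**What the plan says.** Placebo-controlled SAP 5.1.1 states that efficacy data from scheduled and unscheduled visits are "mapped to an appropriate analysis visit using the windowing scheme shown in Tables 2-6". The relevant final windows are:

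- Table 3 (MDS-UPDRS Part II, CGI, cognitive composite, PSP-QoL, RBANS): "Week 52 | 365 | [309, 378", that is, Days 309 to 378.
- Table 2 (PSPRS): "Week 52 | 365 | [351, 378", that is, Days 351 to 378.

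OLE SAP 5.2 repeats both limits. Its next window is Week 64, from Day 407, in Tables 1 and 2(a). In Table 3(b), for the 13 cognitive subtests, the next window is Week 76, from Day 449.

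Section 5.2.4.5 lists out-of-window values among the causes of missing data and handles them as missing at random, which is also the assumption of the main model in 5.1.4.

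Other final windows in the same SAP run later: "Week 48 | 337 | [295, 434" in Table 4, "Week 52 | 365 | [281, 448" for volumetric MRI, "Week 52 | 365 | [351, the end day of the placebo-controlled period" for laboratory data and "Week 52 | 365 | [267, the end day of the placebo-controlled period" for ECG. The OLE laboratory table (OLE SAP 6.3.1, Table 7) sets Week 52 at Days 351 to 406.

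**The concern.** Protocol 7.4 expects dosing visits to be delayed rather than skipped, and footnote d to Protocol Table 2 encourages withdrawn participants to return at Week 52. Some Week 52 assessments may therefore fall after Day 378 but before any open-label dose. They are observed values of the primary endpoint or of endpoints in the fixed testing sequence (5.3.1), and they fit the treatment-policy estimand of 5.2.3. Neither SAP gives a reason for leaving them out.

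A lost PSPRS value has two further effects. The participant counts as a non-responder in 5.2.5.5, and in 5.2.4.3 an extrapolated score replaces the observed one.

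**Working it through.** **1. Limits.** Days early = target minus lower limit; days late = upper limit minus target.

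| Final window | Target | Limits | Early | Late |
|---|---|---|---|---|
| Table 3, Week 52 | 365 | 309-378 | 56 | 13 |
| Table 2, Week 52 | 365 | 351-378 | 14 | 13 |
| Table 4, Week 48 | 337 | 295-434 | 42 | 97 |
| MRI, Week 52 | 365 | 281-448 | 84 | 83 |
| OLE laboratory, Week 52 | 365 | 351-406 | 14 | 41 |

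Gap before OLE Week 64: 407 - 378 - 1 = 28 days (Days 379-406). For the subtests in OLE Table 3(b): 449 - 378 - 1 = 70 days (Days 379-448).

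**2. Where the limits come from.** A window that starts at the midpoint between scheduled visits gives:

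- Week 36/52: (253 + 365)/2 = 309, the Table 3 lower limit.
- Week 52/64: (365 + 449)/2 = 407, the OLE Week 64 lower limit, so Week 52 should end at Day 406.
- Week 48/76: (337 + 533)/2 = 435, so Table 4 correctly ends at Day 434.
- Week 52/56: (365 + 393)/2 = 379, which reproduces Day 378. Protocol Table 3 schedules none of these scales at Week 56.

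**3. Key secondary endpoints, whole schedule s days late.** Week 52 falls on Day 365 + s and Week 36 on Day 253 + s. The Week 52 cell is empty when 365 + s > 378 and 253 + s < 309, that is, s = 14 to 55. With a limit of Day 406 it is empty only for s = 42 to 55.

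For the composite with s = 14 to 41, the Week 48 letter-number and fluency tests fall on Days 351-378, inside the window, while RBANS falls on Days 379-406, outside it. Two of the three domains contain only RBANS subtests, so under 5.3.1.3 no composite is calculated.

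**4. PSPRS.** The cell is lost when Week 52 falls after Day 378 and no Week 48 value falls on Days 351-378. Examples:

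- Week 52 slips 14 days or more while Week 48 slips less than 14.
- There is no Week 48 value.
- The whole schedule runs 42 days or more late (at s = 42, Week 48 is on Day 379 and Week 52 on Day 407).

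A uniform delay of 14 to 41 days does not empty the cell, because the Week 48 assessment fills it.

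**5. Size.** The plan's power figure reproduces: 230 against 115 completers, difference 3.2, SD 9.95, two-sided 0.05, noncentral t gives 80.2%. The late fraction m and the correlation r with the previous visit are assumptions. The variance factor is r² + (1 - r²)/(1 - m), and the SE factor is its square root. At m = 5%, r = 0.8: 0.64 + 0.36/0.95 = 1.0189, so SE rises 0.94%.

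| m | Key secondary, SE increase (r = 0.8 to 0.6) |
|---|---|
| 2% (about 7 of 345) | 0.4-0.7% |
| 5% (about 17) | 0.9-1.7% |
| 10% (about 35) | 2.0-3.5% |

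For PSPRS, with r = 0.9 to 0.8, power becomes 80.1-80.0% at m = 1%, 80.0-79.9% at 2% and 79.8-79.4% at 5%. If earlier visits recovered nothing, a 5% loss would give 78.1%.

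Responder rates, assuming a normal change with mean 11.39 and SD 9.95: 29.4% at the 6-point threshold and 48.4% at 11 points. At m = 5% they fall by 0.05 × 29.4 = 1.5 and 0.05 × 48.4 = 2.4 percentage points.

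In 5.2.4.3 the amount added from Week 48 is 11.39 × (1 - 48/52) = 0.88 points (15-item: 9.34 × 4/52 = 0.72).

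**The case against.** The best defence is that Day 378 looks chosen. It is the last day before the midpoint to Week 56 on the 4-weekly grid, the OLE vital-signs table uses the same limit, and a tight upper limit suits an endpoint measured just before open-label dosing. The OLE SAP repeats Day 378 for efficacy while writing Day 406 for laboratory data. No rule is broken, since the requirement of windows without gaps appears only in the safety sections. The MRI windows are an imperfect model, because they leave Days 253-280 unmapped.

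This lowers the weight of the point, but it supplies no documented reason to discard pre-extension values. A footnote can exclude post-dose values directly.

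Exposure is also uncertain. The visit tolerance is ±3 days, Protocol 7.4 calls a delay of two weeks or more unusual, and nothing says that later visits are re-anchored after a delay. That stands.

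Three stronger readings are tempting but unsupported:

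- A reader might take 56 days early against 13 late as the fault. The early limit is the ordinary midpoint; only the gap is at issue.
- A reader might infer bias. Nothing shows that lateness differs between blinded arms.
- A reader might infer that the primary endpoint is exposed as often as the key secondary ones. It usually is not, because a late Week 48 PSPRS can fill the cell.

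**Conclusion.** The point holds as a low-priority improvement. The window limits and the unmapped Days 379-406 are certain. That such values count as missing follows from the mapping rule together with 5.2.4.5; section 5.1.1 does not say it outright. The loss is one of precision: at most 3.5% in SE for a key secondary endpoint, and under one percentage point of power for PSPRS, over the ranges assumed. How many participants are affected cannot be learned from the documents.

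**What to change.** Set the Week 52 upper limit to Day 406 in placebo-controlled Tables 2 and 3 and in OLE Tables 1, 2(a) and 3(b). Add one footnote: for participants who enter the extension, only assessments made before the first open-label dose count, and same-day pre-dose assessments are kept; for the others, any assessment up to Day 406 counts. Keep the closest-to-target rule.

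Do not borrow the laboratory end-of-period definition. It stops on the day before the first open-label dose and would drop a same-day Week 52 assessment. The baseline row of Table 3, "Most recent non-missing value on or prior to the first dose date", is the better model.

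The change needs no new data collection. Its costs are:

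- **Drift.** A few values will be up to 406 - 365 = 41 days late: 11.39 × 41/365.25 = 1.28 points on the 28-item PSPRS, or 9.34 × 41/365.25 = 1.05 on the 15-item scale. The documents give no annual rate for the key secondary scales.
- **Time since last dose.** If only Week 52 slips, a value may come up to 406 - 337 = 69 days after the Week 48 dose instead of 28. The treatment-policy estimand allows this.
- **What remains.** Uniform delays of 42 to 55 days still leave the Table 3 Week 52 cell empty, and Days 407-448 stay unmapped in OLE Table 3(b). OLE Table 2(a) lists a Week 64 composite and Table 3(b) does not; reconciling them is a separate matter.

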Follicle-Stimulating Hormone	X	Required for post-menopausal women < 55 (Refer to Appendix 4).
	X	Baseline/Screening Version.
Efficacy Assessments		
Progressive Supranuclear Palsy Rating Scale (PSPRS)	X	
Repeatable Battery for the Assessment of Neuropsychological Disease Severity (RBANS)	X	
Montreal Cognitive Assessment (MoCA)	X	
Phonemic Fluency Test	X	
Letter-Number Sequencing (LNS) Test	X	
Color Trails Test (CTT)	X	Randomization will be stratified by country and screening CTT Part 2 score of either less than or equal to 170 seconds, or greater than 170 seconds.
Magnetic Resonance Imaging (MRI)	X	The MRI should be completed at least 14 days prior to first dose to allow for central assessment of image. A repeat MRI may be requested prior to randomization if protocol standards are not yet met. MRI image quality must be determined to be adequate and local interpretation performed to determine eligibility and to rule out any contraindication to lumbar puncture for participants participating in the [REDACTED]

CONFIDENTIAL

The information contained herein may not be used, disclosed, or published without the written consent of Biogen MA Inc.

Procedure	Screening Visit ^a	Notes

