5.1.1. Overall Study Design

The study design schematic is presented in [Figure 1](#). The study will consist of a 52-week double-blind treatment period, which will be followed by a long-term open-label extension period for follow up. Participants will be randomized to receive BIIB092 or placebo. Approximately 459 participants in total will be randomized in a 2:1 ratio to receive BIIB092 or placebo (306 participants active or 153 placebo). In the double-blind treatment period of the study, participants will be dosed approximately once every 4 weeks (Q4W) up to a total of 13 times, with the last dose of study treatment of the double-blind period (Dose 13) administered at Week 48.

At Week 52, participants completing the double-blind treatment period may choose to continue into the open-label extension period of the study. Participants who wish to continue in the open-label extension period will receive the first dose of the open-label study treatment at Week 52. Participants will be dosed approximately once Q4W throughout the duration of the open-label extension period. The duration of the open-label extension period will vary depending on the date of enrollment of the participant in the study. The study is expected to continue until BIIB092 is commercially available, the development program is terminated, or the study is terminated at the discretion of the Sponsor, whichever comes first.

CONFIDENTIAL

The information contained herein may not be used, disclosed, or published without the written consent of Biogen MA Inc.

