3 GENERAL CONSIDERATIONS

3.1 General Methods

This statistical analysis plan (SAP) only covers the analyses for the double-blind placebo-controlled portion of the study. Hereafter, the double-blind, placebo-controlled portion of the study will be referred to as “the study” in the rest of this SAP (e.g., completion of the study means completion of the placebo-controlled portion). A separate SAP will be prepared for the analyses of the open label extension (OLE) period and integrated analyses across both portions of the study. The analyses of selected exploratory endpoints may be documented separately. The term “subject” used in this SAP and in the analyses is equivalent to the term “participant” used in the Protocol.

Summary tables will be presented using descriptive summary statistics. For continuous variables, summary statistics will generally include: number of subjects with data, mean, standard deviation, median, 25% percentile, 75% percentile, minimum and maximum. For categorical variables, this

will generally include: number of subjects randomized or dosed, number with data, and the percent of those with data in each category.

In general, listings will include all data in the placebo-controlled and OLE periods (all data in the study), with an indicator of the study period (screening, placebo-controlled, or OLE) for each record to indicate when the event occurred.

Unless otherwise specified, baseline value is defined as the most recent non-missing measurement collected prior to the first dose. Change from baseline will be defined as post-baseline value minus baseline value.

Unless stated otherwise, all statistical tests will be 2-sided with statistical significance level of 0.05.

The statistical software SAS® will be used for all summaries and analyses.

The health care region used in the analysis (referred as region in this SAP) is defined as:

- US: United States
- Non-US: Australia, Austria, Canada, France, Germany, Greece, Italy, Russian, Spain, United Kingdom, Japan and Korea

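### The volumetric MRI windows can let an on-treatment scan replace a pre-dose baseline, and can count open-label scans as Week 52 placebo data

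*SAP*

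**What the plan says.** Section 5.1.1 of the placebo-controlled SAP, Table 6, gives three windows for volumetric MRI: "Baseline | 1 | <=84", "Week 24 | 169 | [85, 252" and "Week 52 | 365 | [281, 448" (the last two are closed intervals). When a window holds more than one assessment, "the assessment that is closest to the target visit day will be used for analysis", and a tie goes to the later one.

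Section 3.1 of the same SAP sets a pre-dose default: "baseline value is defined as the most recent non-missing measurement collected prior to the first dose". That sentence opens by allowing exceptions to be specified, and Table 6 specifies one. Tables 2 to 4, for the clinical and cognitive scales, instead use: "Most recent non-missing value on or prior to the first dose date".

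On timing, Protocol Table 1 states "The MRI should be completed at least 14 days prior to first dose", and its footnote places screening procedures within 42 days before first dose. Protocol Section 5.1.1 says that participants who continue "will receive the first dose of the open-label study treatment at Week 52".

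The open-label extension (OLE) SAP repeats the same MRI baseline and Week 52 rows in its Table 5.

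**The concern.** Two features of Table 6 can put a scan in the wrong analysis category.

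- **Baseline.** The nearest-to-target rule works against a screening scan, which must be at least two weeks before Day 1. A scan taken soon after dosing is nearer and wins, although it is no longer a pre-treatment measurement.
- **Week 52.** The window does not stop when open-label treatment starts. The laboratory, ECG and anti-drug antibody tables of the same SAP (Tables 8, 10 and 13) close their last window on the last day of the placebo-controlled period, defined as the day before first open-label dosing for those who continue. Table 6 has no such limit, so a programmer following it would take a post-switch scan in a placebo participant as the Week 52 placebo value.

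At stake is the treatment comparison of change in brain volume, a secondary endpoint. The primary PSPRS analysis uses a different window table and is untouched.

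**Working it through.** **Inputs.** Windows, target days and tie rule: placebo-controlled SAP Section 5.1.1 and Table 6. Screening limits of 14 and 42 days: Protocol Table 1 and its footnote. Week 52 visit tolerance of ±3 days: Protocol Table 2. Dosing every 28 days from Day 1, with open-label dosing from Week 52: Protocol Section 5.1.1.

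**Reproducing the plan's figures.** Target day = 7 × week + 1, so Week 24 is 7 × 24 + 1 = 169 and Week 52 is 7 × 52 + 1 = 365. Each window is target − 84 to target + 83:
- Week 24: 169 − 84 = 85 and 169 + 83 = 252.
- Week 52: 365 − 84 = 281 and 365 + 83 = 448.
- Baseline upper limit: 1 + 83 = 84.

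The table is reproduced exactly. It applies one template that takes no account of the first dose or of the start of open-label treatment.

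**Which on-treatment scans displace a screening scan.** Let the screening scan be s days before first dose. A scan on Day d is d − 1 days from Day 1. It is chosen if d − 1 ≤ s, with equality included because ties go to the later scan. So d ≤ s + 1.

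| Screening scan | Displaced by a scan up to | Share of Day 1 to Day 365 |
|---|---|---|
| 14 days before dosing | Day 15 | 14/364 = 3.8% |
| 42 days before dosing | Day 43 | 42/364 = 11.5% |

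The limits move by one day if the programmed day count includes a Day 0, hence "about" elsewhere in this note. Scheduled doses up to Day 43 fall on Days 1 and 29.

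**Week 52 tail.** 448 − 365 = 83 days after nominal first open-label dosing. With the ±3-day tolerance this is 448 − 368 = 80 to 448 − 362 = 86 days. Open-label doses fall due on Days 365, 393 and 421 in that interval.

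**Days in no window.** From 252 + 1 = 253 to 281 − 1 = 280, which is 28 days. The midpoint of the two targets, (169 + 365)/2 = 267, lies inside.

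**The case against.** The strongest reply is that neither event should be common. Repeat screening scans are to be requested before randomization. The double-blind schedule has scans only at Weeks 24 and 52, with none at Early Discontinuation. Section 5.3.2.8 restricts the endpoint to scans passing QC on the scanner used at screening. Section 3.1 also limits this SAP to the double-blind period. The first three points stand as limits on frequency, but the scanner condition does not bar an on-treatment baseline. The scope statement suggests that open-label scans were not intended, yet Table 6 does not exclude them. Tables 2 to 4 also run past Day 365 (to Day 378, or Day 434 for Week 48), so the missing cut-off is not peculiar to MRI. That does not justify it here.

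Several stronger readings are tempting and do not hold:

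- *That 84 days, about 23% of the year (84/365), could be absorbed in place of a valid baseline.* With a compliant screening scan, displacement stops at about Day 43. Day 84 is reachable only when no usable pre-dose scan exists, and then nothing valid is replaced.
- *That the bias is toward zero.* On-treatment baselines confined to the BIIB092 arm would shrink that arm's apparent change and exaggerate benefit. Under the Protocol's hypothesis of slowed progression, placebo participants scanned late have accrued extra change. If only they are late, the difference widens. If both arms are equally late, the Day 365 difference is roughly carried forward.
- *That Days 253 to 280 were left out by mistake.* The gap follows from the −84/+83 template, and declining to label a scan 12 or more weeks off target is defensible. The no-gap rule in Section 6.1.2 is written for safety windows.
- *That every other efficacy table demands a pre-dose baseline.* Table 5 carries a redacted exception, so only Tables 2 to 4 can be cited.

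**Conclusion.** The point holds as a minor specification defect. Followed literally, Table 6 can substitute an on-treatment scan for a valid pre-dose one, up to about Day 15 to Day 43 depending on when screening MRI was done. It can also admit scans up to 83 days (80 to 86 with visit tolerance) after open-label dosing starts into the double-blind Week 52 comparison.

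This assumes that screening MRI kept to the 14- and 42-day limits, that the nearest-scan rule applies to MRI as written, and that the participant had an unscheduled early scan or, for Week 52, entered the extension with a scan only after the switch. The documents give no count of such participants. The schedule suggests few.

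The p-values are nominal (Section 5.3.2), no direction of bias can be asserted, and no conclusion on the primary or key secondary endpoints depends on this.

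**What to change.** In placebo-controlled SAP Table 6:

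- **Baseline row:** the last scan passing endpoint QC on or before first dose, taken pre-dose.
- **Week 52 row:** keep the lower limit of Day 281. Close the window at the earlier of Day 448 and the first open-label dose, retaining a scan taken on the day of that dose but before it. For participants who do not enter the extension, Day 448 still applies.
- **Lower limits of Week 24 and Week 52:** leave unchanged. Opening Week 24 to any post-dose scan, or starting Week 52 at Day 267, would create new mislabelling.

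Make the same baseline edit in OLE SAP Table 5. It is less urgent there, because Section 5.3 of that SAP says efficacy MRI will not be analysed at the interim.

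The cost is a few table cells and matching programming, with no new data collection. A participant with no usable pre-dose scan would have no MRI baseline and would drop out of the change analysis; the number should be reported. Settling the rule before results are seen avoids a later choice about which scans count.
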